	
 • Proportion of subjects dying from any cause over an assessment period from start of study treatment until Day 28. • Proportion of subjects requiring mechanical ventilation over an assessment period from start of study treatment until Day 28. • Time (number of days) to negative conversion (defined as viral load <100 copies) of detectable SARS-CoV-2 viral RNA (defined as viral load \geq100 copies) in RT-PCR assays of saliva, from start of study treatment to study day 10. Included: all subjects with a positive PCR on study day 1 or 2 or 3. The endpoint will be assessed from study day 3 onward. • Time to Sustained Clinical Recovery defined as number of days from start of study treatment to Sustained Alleviation of Symptoms, evaluated from study day 3 onward. • Proportion of subject with COVID-19 progression, where progression is defined as the occurrence at any point from study day 1 to study day 28 of emergency department (ED) visit for any reason OR hospitalization for any reason. • Proportion of subjects with COVID-19 progression, where progression is defined as the occurrence from study day 3 onward of any emergency department (ED) visit for COVID-19 worsening or shortness of breath OR hospitalization for COVID-19 worsening or shortness of breath OR death (narrow progression) • Proportion of subjects with COVID-19 progression, defined as the occurrence from study day 3 onward of any ED visit for COVID worsening or shortness of breath OR hospitalization for COVID worsening or shortness of breath OR death OR the development of symptomatic worsening from study day 3 onward (defined as \geq2 additional COVID symptoms at a level of moderate or severe which have not existed (at any level of severity) at baseline or fever (temperature of \geq38.0°C) which has not existed at baseline or oxygen desaturation (O2 saturation <94%) which has not existed at baseline) (Broad progression). 
Safety endpoint:
 
 • Number (and proportion) of patients reporting treatment emergent adverse events (TEAEs) (by MedDRA system organ class and preferred term). • Number (and proportion) of patients reporting serious treatment emergent adverse events (TEAEs) (by MedDRA system organ class and preferred term). • Vital Signs including oral temperature, heart rate, oxygen saturation with height and weight. • Clinical laboratory tests including Biomarkers, Chemistry, Coagulation and Hematology.

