For any subject who has incompletely submitted relevant data to assess clinical recovery, the primary endpoint is met on the first day from study day 1 onward where clinical recovery is reached, defined as none of the symptoms is worse than mild, as well as temperature $<38.0^{\circ}\text{C}$ and O2 saturation $\geq 94\%$, and considered sustained over the 3 following days when there is no known flare up of symptoms beyond mild. During the 3-day sustainability period, complete COVID symptom data (not including taste, smell) is required for at least 2 of the 3 days (COVID-19 symptom data can be missing for 1 of the first two sustainability days but not for the last day of sustainability). Missing information for temperature or O2 saturation during the 3-day sustainability period will not invalidate reaching the endpoint.

For any subject who has been lost to follow-up prior to Day 28, the investigators will make reasonable efforts to determine whether the subject has been admitted to the hospital or died up to Day 28. For subjects who experienced sustained clinical recovery prior to Day 28 and lost to follow-up, should the investigator be able to confirm no admission to the hospital and no death, the subject will be flagged as having the endpoint of sustained clinical recovery. Subjects who were lost to follow-up and for whom the investigator could not confirm lack of admission to the hospital or death before Day 28, will be flagged as the worst possible outcome regardless of clinical recovery.

Secondary Endpoints:**Key Secondary Efficacy Endpoint:**

- Proportion of subjects with COVID-19 progression, where progression is defined as the occurrence from study day 1 onward of any emergency department (ED) visit for COVID-19 worsening or shortness of breath **OR** hospitalization for COVID-19 worsening or shortness of breath **OR** death (narrow progression)

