- Proportion of subjects with COVID-19 progression, defined as the occurrence from study day 1 onward of any ED visit for COVID worsening or shortness of breath **OR** hospitalization for COVID worsening or shortness of breath **OR** death **OR** the development of symptomatic worsening from study day 1 onward (defined as ≥ 2 additional COVID symptoms at a level of moderate or severe which have not existed at baseline or fever (temperature of $\geq 38.0^{\circ}\text{C}$) which has not existed at baseline or oxygen desaturation (O₂ saturation $<94\%$) which has not existed at baseline) (broad progression).

Viral Shedding Sub-Study:

- Time (number of days) to negative conversion (defined as undetectable viral load) of detectable SARS-CoV-2 viral RNA in RT-PCR assays of saliva, from start of study treatment to date of last viral assessment. Included: all subjects with a positive PCR on study day 1 or 2 or 3. The endpoint will be evaluated from study day 1 onward.

Additional Secondary Efficacy Endpoints

- Time (number of days) to negative conversion of positive SARS-CoV-2 viral culture assays of saliva, from start of study treatment to date of last viral assessment. Subjects with a positive saliva SARS-CoV-2 PCR on any study day will have viral cultures performed. Subjects with a positive viral culture on study day 1 or 2 or 3 will be included in this analysis. The endpoint will be evaluated from study day 1 onward.

Exploratory Endpoints (details of the planned analyses are described in SAP 3.1):

- Proportion of subjects showing sustained clinical recovery by study Day 1, 3, 5, 7, 10, 14, 21.
- Proportion of subjects showing resolution of Symptoms by Days 1, 3, 5, 7, 10, 14, 21, where resolution is defined as symptom severity of 0 for all symptoms as well as temperature of $<38.0^{\circ}\text{C}$ as well as oxygen saturation of $\geq 94\%$.
- Proportion of patients showing negative conversion of detectable SARS-CoV-2 viral RNA in saliva on study day 1 or 2 or 3 to undetectable viral load on Study Days 3, 5, 7, and 10. Included: all subjects with a positive PCR on study day 1 or 2 or 3.
- Proportion of patients showing negative conversion of positive SARS-CoV-2 viral culture in saliva on Study Days 3, 5, 7 and 10. Subjects with a positive saliva SARS-CoV-2 PCR on any study day

will have viral cultures performed. Subjects with a positive viral culture on day 1 or 2 or 3 will be included in this analysis.

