- Proportion of subjects dying from any cause over an assessment period from start of study treatment until Day 28.
- Proportion of subject with COVID-19 progression, where progression is defined as the occurrence at any point from study day 1 to study day 28 of emergency department (ED) visit for any reason OR hospitalization for any reason.
- Proportion of subjects requiring mechanical ventilation over an assessment period from start of study treatment until Day 28.
- Time (number of days) to negative conversion (defined as viral load <100 copies) of detectable SARS-CoV-2 viral RNA (defined as viral load >100 copies) in RT-PCR assays of saliva, from start of study treatment to date of last viral assessment. Included: all subjects with a positive PCR on study day 1 or 2 or 3. The endpoint will be assessed from study day 3 onward.
- Time to Sustained Clinical Recovery defined as number of days from start of study treatment to Sustained Alleviation of Symptoms, evaluated from study day 3 onward.
- Proportion of subjects with COVID-19 progression, where progression is defined as the occurrence from study day 3 onward of any emergency department (ED) visit for COVID-19 worsening or shortness of breath OR hospitalization for COVID-19 worsening or shortness of breath OR death (narrow progression)
- Proportion of subjects with COVID-19 progression, defined as the occurrence from study day 3 onward of any ED visit for COVID worsening or shortness of breath OR hospitalization for COVID worsening or shortness of breath OR death OR the development of symptomatic worsening from study day 3 onward (defined as >2 additional COVID symptoms at a level of moderate or severe which have not existed (at any level of severity) at baseline or fever (temperature of $\geq 38.0^{\circ}\text{C}$) which has not existed at baseline or oxygen desaturation (O2 saturation <94%) which has not existed at baseline) (Broad progression).

Safety Endpoint:

1. Number (and proportion) of patients reporting treatment emergent adverse events (TEAEs) (by MedDRA system organ class and preferred term). See additional information on assessing adverse events under section 9.4.
2. Number (and proportion) of patients reporting serious treatment emergent adverse events (TEAEs) (by MedDRA system organ class and preferred term).
3. Vital Signs including oral temperature, heart rate, oxygen saturation with height and weight.

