10.5 Analysis of the Primary Efficacy Endpoint(s)

For the primary efficacy endpoint, time to sustained clinical recovery from study day 1 onward will be compared using a Gehan Wilcoxon test.

The primary analysis of the primary efficacy endpoint will be based on the Modified Intent to Treat Population (mITT), defined as any subject randomized into the study and took at least one dose of study medication (excluding subjects who qualified for enrollment based upon changes in taste and smell).

Additional primary efficacy endpoint analyses will also be performed using the mITT, mITT2, and the Per Protocol populations. Every effort will be made to ensure that subjects are followed until hospitalization, death, or 28 days post treatment start, whichever happens first. Subjects who were hospitalized or died will be assumed to have not met the primary endpoint in the primary analysis.

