10.9 Exploratory Analyses

Exploratory endpoints are related to proportion of subjects and will be presented with counts and percentage. Significance among group will be evaluated using Chi-Square test or Fisher test as applicable. The corresponding confidence interval for the difference in proportions will be calculated.

A detailed description of all statistical analyses is described in the SAP 3.1.

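### The exploratory any-reason COVID-19 progression endpoint omits death, so a subject who dies without an ED visit or admission is counted as not progressed

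*Combined protocol and SAP*

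**What the plan says.** In section 4.0 (Exploratory Endpoints) the protocol lists a proportion of subjects with COVID-19 progression whose only components are "emergency department (ED) visit for any reason OR hospitalization for any reason". The synopsis in section 2.1 gives the same two components over the same window: "study day 1 to study day 28 of emergency department (ED) visit for any reason OR hospitalization for any reason".

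The narrow version ends differently: "hospitalization for COVID-19 worsening or shortness of breath OR death (narrow progression". Death carries no restriction on cause there. Broad progression also includes death and adds symptomatic worsening. Both versions appear twice, as key secondary endpoints from study day 1 and as exploratory endpoints from study day 3.

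Mortality is also an exploratory endpoint of its own: "Proportion of subjects dying from any cause over an assessment period from start of study treatment until Day 28".

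For exploratory proportions, section 10.9 gives the test and no rule for deaths: "Significance among group will be evaluated using Chi-Square test or Fisher test as applicable". Section 4.0 refers the reader elsewhere for more: "Exploratory Endpoints (details of the planned analyses are described in SAP 3.1".

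**The concern.** The endpoint carries the same label as narrow progression and drops the requirement that the ED visit or admission be due to COVID-19 worsening or shortness of breath. Removing a restriction on cause would be expected only to add events. Because death is also dropped, the change can remove an event as well, and the one removed is the most severe.

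Two results tables, both headed COVID-19 progression, could then classify the same deceased subject in opposite ways. If such deaths were unevenly split, the arm with more of them would look better in the any-reason table than it should. The situation can arise in this design: subjects are outpatients, and section 5.1 makes every contact remote except Days 1 and 10.

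**Working it through.** The plan states no figure for this endpoint, so there is none to reproduce. The check compares the definitions, then puts a scale on the gap.

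**Components, from sections 2.1 and 4.0**

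| Endpoint | Tier | ED visit or hospitalization | Death |
|---|---|---|---|
| Narrow, from day 1 | key secondary | COVID-19 worsening or shortness of breath | included |
| Broad, from day 1 | key secondary | same, plus symptomatic worsening | included |
| Narrow, from day 3 | exploratory | COVID-19 worsening or shortness of breath | included |
| Broad, from day 3 | exploratory | same, plus symptomatic worsening | included |
| Any-reason, days 1 to 28 | exploratory | any reason | **not included** |

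**How individual subjects are classified (narrow from day 1 against any-reason, within days 1 to 28)**

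1. Survivor with a COVID-19-related ED visit or admission: event on both.
2. Survivor whose only ED visits or admissions had other causes: event on any-reason only.
3. Death after an ED visit or admission: event on both.
4. Death with no ED visit or admission: event on narrow only.

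Case 4 shows that narrow events are not a subset of any-reason events. Against the exploratory narrow version, the same holds for deaths on day 3 or later.

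**Search for a rule that would count case 4**

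- Section 10.5 has such a rule, but for the recovery endpoint: "Subjects who were hospitalized or died will be assumed to have not met the primary endpoint in the primary analysis".
- The worst-outcome rule for subjects lost to follow-up in section 4.0 also concerns the primary endpoint.
- Sections 10.4, 10.6 and 10.9 give tests and summaries and say nothing on deaths for this endpoint.

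**When the any-reason count would be the smaller**

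Let d be the number of subjects in case 4 and s the number in case 2. Then any-reason count − narrow count = s − d. The any-reason count is lower only if d > s.

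**Scale**

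- Planned subjects per arm: 625 (section 5.1).
- One case-4 death: 1/625 = 0.0016, or 0.16 percentage points.
- Rate of such deaths: not given. Assumed range of 0 to 3 in one arm: 0/625 to 3/625, or 0 to 0.48 percentage points.

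The analysed denominator may be somewhat below 625, so these are approximate.

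**The case against.** The strongest reply is that the endpoint is meant to measure health-care use. The study objective concerning hospitalizations and ED visits (sections 2.1 and 4.0) does not mention death either, and the omission is identical in the synopsis and the body, which suggests a choice and not a slip. This reading is possible but weak. The endpoint is labelled progression, not health-care use, and the progression endpoint that corresponds to that same objective, narrow progression, does include death. If use of care is what is meant, the label and the handling of deaths still need stating.

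A second reply is that deaths are visible elsewhere. This stands. All-cause mortality to Day 28 is a separate exploratory endpoint, death counts in both key secondary progression endpoints, and it is a failure for the primary endpoint. A reader might infer that deaths disappear from the trial's reporting; they do not. Separate reporting limits the harm, but it does not change how this composite classifies a death.

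A third reply is that SAP 3.1 may settle the matter. Its text is not in the documents supplied, so this cannot be excluded. The protocol definition would still have to agree with it.

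**Conclusion.** The point holds as a minor defect of definition. On the protocol text, a death without an ED visit or admission is a non-event for the any-reason endpoint and an event for narrow progression.

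Two stronger readings are tempting and are not supported. First, a reader might infer that the endpoint exists to check whether the narrow result depends on how events are attributed, and that it fails in that role. The parallel wording invites this, but the documents give the endpoint no stated purpose. Second, a reader might infer that the any-reason count is likely to fall below the narrow count. That needs deaths without an ED visit or admission to outnumber survivors seen only for other causes, and nothing in the documents makes that likely. The more realistic failure is that a few narrow events are missing from the any-reason count.

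The size is about 0.16 percentage points per such death, and 0 to 0.48 points under the assumed range of 0 to 3 deaths in one arm. The endpoint is not in the testing hierarchy of section 10.6, so no primary or key secondary conclusion is affected. The conclusion rests on the protocol wording and is subject to whatever SAP 3.1 says.

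**What to change.** In sections 2.1 and 4.0, keep the two existing components and the day 1 to day 28 window, and add death from any cause as a third component joined by OR. Make the same change in the SAP wherever the definition is repeated. The any-reason endpoint will then contain every narrow event through Day 28.

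The cost is a few words in each place. Survival status is already documented at the Day 10, follow-up and Day 28 visits (sections 9.2.3 to 9.2.5), and all-cause death to Day 28 is already an endpoint. No new data, visits or subjects are needed, and the alpha allocation is unchanged.

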5.0 STUDY DESIGN

5.1 Overall Design

This is a double-blinded, randomized, placebo-controlled, superiority trial of approximately 1250 adult outpatients with mild to moderate symptoms of COVID-19 not requiring hospitalization. Depending on the site of enrollment, subjects will be identified at COVID-19 testing centers, testing laboratories, or other clinical care settings. As this study will enroll outpatients only, to prevent violating quarantine requirements and decrease risk of COVID-19 for study team members, most study interactions will be performed remotely with no need for study subjects to leave their homes to fulfill their study obligations. Besides study visits on Day 1 and Day 10, which will be in-person, all other study interactions will be done remotely, using telehealth and video conferencing. Study materials will be provided to subjects at their home or in-site.

Subjects in the treatment arm (n= 625) will receive favipiravir orally taken approximately every 12 hours in addition to current standard of care treatment. The first two doses of favipiravir will be 1800 milligrams. The following doses will be 800 milligrams for a total of 10 days of therapy. Those in the control group (n= 625) will receive placebo orally, using the same numbers of tablets on day 1 and the subsequent 9 more days (total 10 days of treatment), in addition to current standard of care treatment. Saliva PCR testing will be performed at an accredited central laboratory. The site's Principal Investigators will be responsible for study recruitment and engaged as deemed necessary by the Study Team to ensure identification and reporting of maximum number of positive cases and prompt subject engagement/enrollment. This study will be listed at www.clinicaltrials.gov.

Subjects who provide informed consent, meet all inclusion and no exclusion criteria will be randomized on Treatment Day 1 in a 1:1 ratio to either the Treatment Group or the Control Group, in accordance with a computer-generated schedule prepared by a biostatistician. The randomization schedule will be incorporated into the Interactive Web Randomization System (IWRS). Randomization will then be performed by study personnel directly in the IWRS system. Study personnel will be instructed not to randomize until subject has been confirmed to meet all inclusion/exclusion criteria on treatment Day 1.

5.2 Scientific Rationale for Study Design

Randomized, double blind, placebo control (RDBPC) studies provide the strongest possible evidence of causation. Phase III trials are used to expand on Phase II research of the efficacy and safety of an intervention in subjects with the disease for which a new intervention is proposed. Randomization in combination with blinding helps to avoid possible bias in the selection of subjects, their assignment to an intervention or control, and the analysis of their response to the intervention.

5.3 Dose Justification and Tablets needed

5.3.1 Justification for Dose

Favipiravir will be taken approximately every 12 hours. The dosage for favipiravir to be used in this study is 1800 mg (9 tablets of 200 mg) orally for the first 2 doses, then 800 mg orally approximately every 12 hours to complete days 2-10 of therapy. Favipiravir is provided as 200 mg tablets and dosed orally. Favipiravir is rapidly and completely absorbed after oral administration of the 200 mg immediate release tablets. Although discouraged, if necessary, favipiravir may be crushed for administration and can be

taken with or without food [24-25]. This dosing strategy is increased from the licensed dosing regimen for influenza, to account for the higher in-vitro concentrations required for activity against SARS-CoV-2. Elevated dosing strategies, up to 6000 mg on day 1 followed by 1200 mg BID has been used in published Favipiravir studies for Ebola [26]. Prolonged administration to 22 days has been explored in a phase 1 study in Japan (JP120) with a favorable safety profile (patients received 1800 mg PO BID on day 1 followed by 800 mg PO BID from day 2-21 and a single dose of 800 mg on day 22).

5.3.2 Number of tablets required for the entire study

For a 10-day course: 1800 mg (9 tablets of 200 mg) x2 doses (a total of 18 tablets), then 800 mg (4 tablets) x2 daily doses until study day 10 (8 tablets per day to complete 10 days of therapy) for a total of 90 tablets per subject for the entire study period. Tablets required for dosing of the entire study population per treatment arm will be 56,250 (625 subjects x 90 tablets per subject).

Considering competitive enrollment involving multiple countries and sites, it is very critical to maintain sufficient quantity of IPs at each IP depot and participating sites. Hence, it would require to add-on approximately 50% contingency quantity. This will make up to total approximately 85,000 tablets for the entire study per each treatment arm.

5.4 Dosing in Special Populations

Favipiravir is contraindicated in nursing mothers and pregnant women or women of child-bearing age who are not taking oral contraception due to its potential teratogenicity. No alteration of dosing is needed in subjects with renal impairment. Total exposure for plasma favipiravir for subjects with severe renal impairment (Stage 4) was 1.3-fold higher compared to subjects with normal renal function. No obvious effect of renal impairment on safety was observed and favipiravir treatment was generally well tolerated in subjects with renal impairment.

No alterations in dosing strategies are required in older adults. The maximum plasma concentration and AUC values in elderly subjects in a single and a multiple-dose study completed in Japan were higher than in young subjects. Comparing AUC values on Day 5, the differences were 40 and 80% after 600 mg once a day and 400 mg BID, respectively. In the companion study completed in the United States of America, there were no differences between young and older populations based on Day 5 AUC comparison in subjects receiving either 600 or 800 mg BID.

